## 16.1.5 Estimation of Pharmacokinetic Parameters

The computer program Phoenix® WinNonlin® version 6.4, or higher (Certara, L.P., [name]) will be used to derive PK parameters applying non-compartmental analysis (NCA).

The statistical software SAS® (Statistical Analysis System, SAS-Institute, Cary NC, USA, windows version 9.1 or higher) may be used to generate additional PK parameters, produce tables, listings and figures.

### 16.1.5.1 Estimation of Pharmacokinetic Parameters in Plasma

PK parameters analysis will be calculated using the actual elapsed time since dosing, with the exception of the interim analysis for SMC. In cases where the actual sampling time is missing, calculations may be performed using the scheduled time. Details (e.g. number of samples, participants affected) will be described in the CSR. In cases actual dosing time is missing, scheduled time might be used for NCA after performance of adequate plausibility checks and agreement with the sponsor. Decision and rationale should be included in the CSR.

The following plasma PK parameters will be calculated for M4076 where appropriate

Symbol	Definition
AUC 0-tlast	The area under the concentration-time curve (AUC) from time zero (= dosing time) to the last sampling time ( $t_{last}$ ) at which the concentration is at or above the lower limit of quantification. Calculated using the mixed log-linear trapezoidal rule (linear up, log down).
AUC 0-tlast /Dose	The Dose normalized AUC from time zero to the last sampling time ( $t_{last}$ ) at which the concentration is at or above the lower limit of quantification. Normalized using the actual dose, using the formula $AUC_{0-t_{last}} / \text{Dose}$ .
AUC <math>\tau</math>	The AUC over the dosing interval from $T1=0$ h to $T2=\tau$ h. Calculated using the mixed log-linear trapezoidal rule (linear up, log down). For single dose, $AUC_{\tau}$ is calculated as a partial area with the defined time range. In multiple dose profiles $AUC_{\tau}$ is calculated at steady state from one pre-dose time point to the dosing interval time. In cases where the actual observation time is not equal to the scheduled observation time $AUC_{\tau}$ will be calculated based on the estimated concentration at $\tau$ hours, and not the concentration at the actual observation time where a regression has been performed.
AUC <math>\tau</math> /Dose	The dose normalized AUC over the interval from $T1=0$ h to $T2=\tau$ h. Normalized using actual dose, using the formula $AUC_{\tau} / \text{Dose}$ .
AUC 0-72	The AUC from time zero (= dosing time) to 72 hours post-dose. Calculated using the mixed log-linear trapezoidal rule (linear up, log down). In cases where the actual observation time is not equal to the scheduled observation time (72 hours), $AUC_{0-72}$ will be calculated based on the estimated concentration at 72 hours, and not the concentration at the actual observation time (Part 1B only).
AUC 0-72 /Dose	The dose normalized AUC from time zero (= dosing time) to 72 hours post-dose. Normalized using actual dose, using the formula $AUC_{0-72} / \text{Dose}$ . (Part 1B only)
AUC 0-<math>\infty</math>	The AUC from time zero (dosing time) extrapolated to infinity, based on the predicted value for the concentration at $t_{last}$ , as estimated using the linear regression from $\lambda_z$ determination. $AUC_{0-\infty} = AUC_{0-t_{last}} + C_{last \text{ pred}} / \lambda_z$ (single dose only)
AUC 0-<math>\infty</math> /Dose	The dose normalized AUC from time zero extrapolated to infinity. Normalized using actual dose, using the formula $AUC_{0-\infty} / \text{Dose}$ . (single dose only)
CL/F	The apparent total body clearance of study intervention following extravascular administration. $CL/F = \text{Dose p.o.} / AUC_{0-\infty}$ . (single dose)
C max	Maximum observed concentration
C max /Dose	The dose normalized maximum concentration. Normalized using the actual dose, and the formula $C_{max} / \text{Dose}$ .
C trough	The concentration observed immediately before next dosing (Part 1A only)
LI	The linearity index after repeated administration calculated as $LI = (AUC_{\tau} \text{ after multiple dose}) / (AUC_{0-\infty} \text{ after single dose})$ (Part 1A, Day 8 only)
R acc(AUC<math>\tau</math>)	The accumulation ratio after repeated administration calculated as $R_{acc}(AUC_{\tau}) = (AUC_{\tau} \text{ after multiple dose}) / (AUC_{\tau} \text{ after single dose})$ (Part 1A, Day 8 only)
R acc(Cmax)	The accumulation factor to assess the increase in maximum concentration until steady state is reached. $R_{acc}(C_{max}) = (C_{max} \text{ after multiple dose}) / (C_{max} \text{ after single dose})$ (Part 1A, Day 8 only)
t 1/2	Apparent terminal half-life. $t_{1/2} = \ln(2) / \lambda_z$
t last	The last sampling time at which the concentration is at or above the lower limit of quantification

$t_{max}$	The time to reach the maximum observed concentration collected during a dosing interval (unless otherwise defined, take the 1st occurrence in case of multiple/identical $C_{max}$ values)
$V_z/F$	The apparent volume of distribution during the terminal phase following extravascular administration. $V_z/F = \text{Dose}/(\text{AUC}_{0-\infty} * \lambda_z)$ following single dose.

The following urine PK parameters will be calculated where appropriate

Symbol	Definition
$Ae_{t1-t2}$	Total amount excreted between times $t_1$ (= start) and $t_2$ (= end) of the current collection interval. Calculated by interval $Ae_{t1-t2} = \text{Conc} * Vu(t_{1-t2})$ and cumulative.
$fe_{t1-t2} \%$	Fraction of administered drug that is excreted unchanged in urine between times $t_1$ (= start) and $t_2$ (= end) of the current collection interval. Calculated by interval $fe_{t1-t2} = Ae_{t1-t2}/\text{Dose}$ and cumulative.
$CL_R$	The renal clearance of study intervention. $CL_R = Ae_{0-t}/\text{AUC}_{0-t}$ .

Additional PK parameters may be calculated where appropriate.

Units for PK parameter output will be based on concentration and dose units used in the study, unless otherwise specified. In case concentration data units change within the study, PK parameters will be reported using consistent units throughout study outputs. In such cases, the Sponsor will specify relevant units for reporting before the final PK evaluation.

The parameters  $C_{max}$ ,  $t_{last}$ , and  $t_{max}$  will be obtained directly from the concentration-time profiles. If  $C_{max}$  occurs at more than one timepoint,  $t_{max}$  will be assigned to the first occurrence of  $C_{max}$ .

In cases where the actual observation time is not equal to the scheduled observation time,  $AUC_\tau$  and  $AUC_{0-72}$ , other partial areas will be calculated based on the estimated concentration at  $\tau$  hours, 72h, and not the concentration at the actual observation time.

The following rules might be applied for calculation of  $AUC_\tau$ ,  $AUC_{0-72}$ , after agreement with the Sponsor:

- In case suitable regression cannot be performed, partial areas may be calculated using the actual sampling time provided it is within 10% of the actual sampling time.
- In cases BLQ concentrations occur at the end of the collection interval, these concentrations might be set to missing for calculations of partial AUCs. This is an exemption to the general BLQ handling rule and should be applied in case its application would result in estimation of implausible partial AUC values. Implausibility is considered in cases partial AUCs were greater than  $AUC_{0-\infty}$ .
- At steady state, the pre-dose concentration may be duplicated and used as the trough concentration for calculation of  $AUC_\tau$  if the sample prior to the next dose is missing and vice versa.

The following PK parameters will be calculated for diagnostic purposes and listed, but will not be summarized:

Symbol	Definition
$\lambda_z$ low	First ( $\lambda_z$ low) time point of the time interval of the log-linear regression to determine $\lambda_z$ .
$\lambda_z$ up	Last ( $\lambda_z$ up) time point of the time interval of the log-linear regression to determine $\lambda_z$ .
$N\lambda$	Number of data points ( $N\lambda$ ) included in the log-linear regression analysis to determine $\lambda_z$ .
Rsq, adj	Adjusted goodness of fit statistic (adjusted Rsq) for calculation of $\lambda_z$
AUC extra%	AUC from time $t_{last}$ extrapolated to infinity given as percentage of AUC 0-∞ . (AUC extra% )
Span ratio	Span ratio of interval over which $t_{1/2}$ was estimated/ $t_{1/2}$

The regression analysis should contain data from at least 3 different time points in the terminal phase consistent with the assessment of a straight line on the log-transformed scale. Phoenix WinNonlin “best fit” methodology will be used as standard. If warranted, further adjustment may be made by the pharmacokineticist, after agreement with the Sponsor. The last quantifiable concentration  $>LLOQ$  should always be included in the regression analysis, while the concentration at  $t_{max}$  and any concentrations BLQ which occur after the last quantifiable data point  $>LLOQ$  should not be used.

If AUCextra%>20% and/or the coefficient of correlation (Rsq adj) of  $\lambda_z$  is <0.8 and/or the observation period over which the regression line is estimated (span ratio) is less than 2-fold the resulting  $t_{1/2}$ , the rate constants and all derived parameters (e.g.  $t_{1/2}$ , AUC0-∞, CL/F etc.) will be listed, flagged and included in the parameter outputs and excluded from descriptive statistics and further statistical evaluation.

If AUC0-∞ cannot be determined reliably for all subjects and/or dose levels/treatments, an alternative AUC measure, such as AUC to a fixed timepoint or AUC0-tlast, may be used in the statistical analysis of dose proportionality and/or food effect.

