^c Efforts should be made to collect blood for PK and CCl [REDACTED] and biopsy samples around similar time points (± 20 minutes).

Cl

Period 1 Day 8/9 PK sampling may be conducted on Day 15/16, or Period 2 Day 1/2, if required for logistical reasons and/or in case study intervention was interrupted and resumed. In this case, timing of associated triplicate ECG measurements should be rescheduled accordingly, and the Sponsor notified in advance.

Table 4

Part 1B Preliminary Food Effect Assessment: Pharmacokinetic, ECG and CCI Assessments

Study Day	M4076 Dosing	PK Sampling Time	Urine Collection for PK	ECG ^b	Paired Biopsies	CCI
Screening (D -28 to -8)					X	
-7	X	Predose ^a	X (1 hour, 0)	X		
		0.5 hour ± 10 minutes postdose	X (0 to 4 hours)			
		1 hour ± 10 minutes postdose		X		
		2 hours ± 10 minutes postdose		X		
		3 hours ± 20 minutes postdose		X		
		4 hours ± 20 minutes postdose	X (4 to 8 hours)	X		
		6 hours ± 20 minutes postdose		X		
		8 hours ± 20 minutes postdose	X (8 to 24 hours)	X		
		10 hours ± 20 minutes postdose				
-6		24 hours ± 2 hours postdose	X (24 to 48 hours)			
-5		48 hours ± 2 hours postdose	X (48 to 72 hours)			
-4		72 hours ± 2 hours postdose				
Day -3 to -1 Washout						

Study Day	M4076 Dosing	PK Sampling Time	Urine Collection for PK	ECG ^b	Paired Biopsies	CCI
Day 1	X	Predose ^a		X		
		0.5 hour ± 10 minutes postdose	X (0 to 4 hours)			
		1 hour ± 10 minutes postdose				
		2 hours ± 10 minutes postdose		X		
		3 hours ± 20 minutes postdose		X		
		4 hours ± 20 minutes postdose	X (4 to 8 hours)	X		
		6 hours ± 20 minutes postdose		X		
		8 hours ± 20 minutes postdose	X (8 to 24 hours)	X		
		10 hours ± 20 minutes postdose				
Day 2		24 hours ± 2 hours postdose	X (24 to 48 hours)			
Day 3		48 hours ± 2 hours postdose	X (48 to 72 hours)			
Day 4 ^d	X	Predose ^a				
		1 hours ± 10 minutes postdose				
		3 hours ± 60 minutes postdose			X ^c	
		6 hours ± 20 minutes postdose				
		8 hours ± 20 minutes postdose				

ECG = electrocardiogram; γ-H2AX = gamma histone family member X; Pd = pharmacodynamic; PK = pharmacokinetic; RDE = recommended dose for evaluation.

^a All predose samples have a window of – 60 minutes prior to next dosing.

- d** Triplicate ECG collection is only applicable to participants dosed in the fasted state. The fasting window in Part 1B is defined as 10 hours predose to 4 hours postdose.

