8.5 Pharmacokinetics

Sampling times for the determination of M4076 can be found in [Table 3](#) for Part 1A and [Table 4](#) for Part 1B. The PK sampling schedule may be modified upon agreement of the clinical pharmacologist, investigators, and SMC to optimize the definition of the pharmacokinetic profiles but will not increase the number of PK draws.

The following PK parameters will be calculated, when appropriate (see [Table 12](#)). A non-compartmental analysis (NCA) will be performed to estimate these PK parameters for M4076.

Table 12 Assessment of Blood Pharmacokinetic Parameters

Symbol	Definition
AUC _{0-t_{last}}	The area under the concentration-time curve (AUC) from time zero (= dosing time) to the last sampling time (t_{last}) at which the concentration is at or above the lower limit of quantification. Calculated using the mixed log-linear trapezoidal rule (linear up, log down).
AUC _{0-t_{last}} /Dose	The Dose normalized AUC from time zero to the last sampling time (t_{last}) at which the concentration is at or above the lower limit of quantification. Normalized using the actual dose, using the formula $AUC_{0-t_{last}}/Dose$.

Symbol	Definition
AUC _τ	The AUC over the dosing interval from $T_1 = 0$ h to $T_2 = \tau$ h. Calculated using the mixed log-linear trapezoidal rule (linear up, log down). For single dose, AUC _τ is calculated as a partial area with the defined time range. In multiple dose profiles AUC _τ is calculated at steady state from one pre-dose time point to the dosing interval time. In cases where the actual observation time is not equal to the scheduled observation time AUC _τ will be calculated based on the estimated concentration at τ hours, and not the concentration at the actual observation time.
AUC _τ /Dose	The dose normalized AUC over the interval from $T_1 = 0$ h to $T_2 = \tau$ h. Normalized using actual dose, using the formula AUC _τ /Dose.
AUC ₀₋₇₂	The AUC from time zero (= dosing time) to 72 hours post-dose. Calculated using the mixed log-linear trapezoidal rule (linear up, log down). In cases where the actual observation time is not equal to the scheduled observation time (72 hours), AUC ₀₋₇₂ will be calculated based on the estimated concentration at 72 hours, and not the concentration at the actual observation time.
AUC ₀₋₇₂ /Dose	The dose normalized AUC from time zero (= dosing time) to 72 hours post-dose. Normalized using actual dose, using the formula AUC ₀₋₇₂ /Dose.

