### 16.1.3 Statistical Analysis of PK Parameter Data

Dose proportionality will be provided separately for  $AUC_{0-\infty}$ ,  $AUC_\tau$ ,  $AUC_{0-tlast}$  and  $C_{max}$  on study day 1 and 8 for Part 1A using a power model. The power model will have the form:

$$Y = a * (dose)^b$$

where Y is the PK parameter, and a and b are the coefficient and exponent, respectively, of the power equation. By taking the natural logarithm (ln), the power model can be analysed using linear regression and has the form:

$$\ln(Y) = \ln(a) + b * \ln(dose) + \text{error}$$

$$= \alpha + \beta * \ln(dose) + \text{error},$$

where  $\alpha$  is the intercept, and  $\beta$  is the slope, and  $\ln(dose)$  is based on the dose size for each subject. For each PK parameter, the point estimate of slope  $\beta$  and its 95% CI will be provided. In addition, the estimated regression line will be overlaid on the individual points in the corresponding scatter plot (log-log scale).

Dose proportionality will be declared if the 90% confidence interval (CI) for  $\beta$  is entirely contained within the critical region,

$$\left( 1 + \frac{\ln(0.50)}{\ln(r)}, 1 + \frac{\ln(2.00)}{\ln(r)} \right)$$

where  $r$  is the ratio of the highest and the lowest dose in a given part of the study. Dose proportionality for participants who were administered the study intervention will be tested for  $C_{max}$  and  $AUC_{0-\infty}$ ,  $AUC_\tau$ ,  $AUC_{0-tlast}$  on Day 1 and at steady state.

Since the study is neither optimally designed nor powered to confirm the presence or absence of meaningful departures from dose proportionality, these results should be interpreted with caution. In addition, graphical assessment would also be considered to understand dose proportionality.

If the samples remain above LLOQ for the whole dosing interval, then  $AUC_{0-t_{last}}$  will be the same as  $AUC_{\tau}$  for Part 1A as there is another dose after 24 hours

A statistical analysis will be conducted to investigate the food effect on the treatment by comparing (fed) treatment to (fasted) treatment for Part 1B.

The natural log (ln)-transformed  $AUC_{0-\infty}$ ,  $AUC_{\tau}$ ,  $AUC_{0-t_{last}}$  and  $C_{max}$  will be analyzed using a mixed effect model. The model will include planned treatment sequence, period, and actual treatment as fixed effects, and subject within planned treatment sequence as a random effect.

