#### **16.1.4 General Specifications for PK Concentration and PK Parameter Data**

Predose samples that occur before the first or subsequent drug administration will be assigned a time of 0 hours, as if the sample had been taken simultaneously with the study intervention administration.

Predose or trough samples which have been taken after the subsequent dosing will be reported as a protocol deviation. The resulting concentrations will be included in concentration listings but excluded from descriptive statistics of concentrations and from PK parameter estimation.

Values below the lower limit of quantification (BLQ) will be taken as zero for summary statistics of PK concentration data, PK parameter estimation (e.g. AUC) and for graphical presentations.

In case profiles have a measurable pre-dose concentration less than or equal to 5% of its  $C_{max}$  value, the participant's data will be included in the PK and statistical analyses without any adjustments. If the pre-dose value is greater than 5% of the  $C_{max}$ , the participant's data for the affected profile will be included in the PK evaluation but excluded from descriptive and further statistical evaluation after agreement with the sponsor.

Missing concentrations (e.g. no sample, insufficient sample volume for analysis, no result or result not valid) will be reported and used generally as "N.R.". A participant who withdraws prior to the last planned observation will be included in the analyses up to the time of discontinuation.

Samples that are collected outside with a time deviation of > 10% from the protocol-scheduled time will be included in the PK parameter estimation (NCA) but will be excluded from the concentration summary and mean/median concentration plots.

PK concentrations which are erroneous due to a sampling processing or analytical error (as documented in the bioanalytical report) may be excluded from the PK analysis if agreed by the Sponsor. In this case the rationale for exclusion will be provided in the CSR. Any other PK concentrations that appear implausible to the Clinical Pharmacologist/Clinical PK/PD Scientist will generally not be excluded from the analysis and data handling will be agreed with the sponsor clinical pharmacologist/PK scientist. Any implausible data will be documented in the CSR.

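### The 10% tolerance for computing AUCτ and AUC0-72 to the actual sampling time compares that time with itself, so it sets no limit on mistimed end-of-interval samples

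*SAP*

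**What the plan says.** SAP 16.1.5.1 first sets a default for partial areas. "In cases where the actual observation time is not equal to the scheduled observation time", AUCτ and AUC0-72 are to use the concentration estimated at τ or at 72 h. Protocol 8.5, Table 12, has the same default; AUC0-72 "will be calculated based on the estimated concentration at 72 hours, and not the concentration at the actual observation time". The protocol has no alternative to this.

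The SAP then adds fallback rules, which are optional and need the Sponsor's agreement: "The following rules might be applied for calculation of" AUCτ and AUC0-72. The first begins "In case suitable regression cannot be performed" and continues that "partial areas may be calculated using the actual sampling time provided it is within 10% of the actual sampling time".

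The SAP's other 10% timing rule, in 16.1.4, uses a different reference. Samples "with a time deviation of > 10% from the protocol-scheduled time will be included in the PK parameter estimation (NCA"), and are dropped only from the concentration summaries and the mean and median plots.

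AUCτ is used in several places. It enters the dose-proportionality power model for Part 1A (Days 1 and 8). In Part 1B its logarithm is among the parameters that "will be analyzed using a mixed effect model" (both in SAP 16.1.3). It is also in the accumulation ratio and the linearity index (SAP 16.1.5.1).

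**The concern.** The clause is meant to stop an area over a clearly different interval from being reported as AUCτ or AUC0-72. As worded, both sides of the comparison are the actual sampling time, so the test cannot fail. The fallback applies when the terminal slope cannot be used to bring the profile to the nominal end of the interval, which is when a limit on the timing error is most needed.

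At stake is comparability between profiles. AUCτ values over unequal intervals could be pooled in a cohort of about three, regressed on dose, or divided by one another to give an accumulation ratio, with nothing in the plan saying how unequal is too unequal.

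**Working it through.** **1. The rule as written and as evidently meant.** Let t be the actual end time and T the scheduled one. As written, the deviation is |t − t| / t = 0% for every t. Against the scheduled time it is |t − T| / T, and a 10% limit gives:

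- T = 24 h: 24 × 0.9 = 21.6 h to 24 × 1.1 = 26.4 h.
- T = 72 h: 72 × 0.9 = 64.8 h to 72 × 1.1 = 79.2 h.

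| Nominal | Actual | Deviation, as written | Deviation from scheduled | Within 10% of scheduled? |
|---|---|---|---|---|
| 24 h | 18 h | 0% | 25.0% | No |
| 24 h | 20 h | 0% | 16.7% | No |
| 24 h | 22 h | 0% | 8.3% | Yes |
| 24 h | 26 h | 0% | 8.3% | Yes |
| 24 h | 28 h | 0% | 16.7% | No |
| 72 h | 70 or 74 h | 0% | 2.8% | Yes |

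**2. Does another rule supply the limit?**

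- SAP 16.1.4 (10% from scheduled) keeps mistimed samples in the parameter estimation.
- The terminal-slope criteria in SAP 16.1.5.1 (extrapolation above 20%, adjusted R² below 0.8, span ratio below 2) remove the rate constants and parameters derived from them. They do not address a partial area computed because regression failed.
- The steady-state substitution in SAP 16.1.5.1 covers a missing pre-dose or trough sample, not a mistimed one, and not single-dose profiles.
- SAP 10.2.1 and 16.1.4 allow values to be flagged or excluded after data review or for important deviations, case by case and without a threshold.

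None of these gives a number.

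**3. Can the timing be far off?** In Part 1B the window is "24 hours ± 2 hours postdose" (protocol Table 4), and 2/24 = 8.3%, inside 10%. In Part 1A, Table 3 ties the Day 2 and Day 9 samples to the next dose (up to 60 minutes before it), so their distance from the previous dose depends on when that next dose is given. Several alternate schedules in protocol Appendix 7 allow 24 ± 4 h, and 4/24 = 16.7%.

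**4. Size, by illustration.** The documents give no half-life. Assume mono-exponential decline with half-lives of 5, 10 and 24 h. Then

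AUC(0–t) / AUC(0–24) = (1 − e^(−kt)) / (1 − e^(−24k)), with k = ln 2 / half-life.

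For t = 18 h:

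- 5 h: (1 − 0.0825) / (1 − 0.0359) = 0.952
- 10 h: (1 − 0.2872) / (1 − 0.1895) = 0.879
- 24 h: (1 − 0.5946) / (1 − 0.5000) = 0.811

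Under this model the ratios also hold at steady state, where the whole curve is scaled by a constant. For an over-long interval, t = 28 h gives 1.016, 1.057 and 1.109.

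**5. What that does downstream.** One such 18 h value in a cohort of three multiplies the geometric mean by the cube root: 0.98, 0.96 and 0.93. If it is the Day 1 value, that participant's AUCτ accumulation ratio is multiplied by 1/0.952 = 1.05, 1/0.879 = 1.14 and 1/0.811 = 1.23.

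**6. What the limit would leave.** At 21.6 h the same formula gives 0.985, 0.958 and 0.928; at 26.4 h, 1.011, 1.036 and 1.067. The corrected limit therefore holds the timing error to about 7% either way under these assumptions.

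**The case against.** The best defence is that this is a plain slip. The paragraph above the clause sets actual against scheduled time, 16.1.4 measures its 10% from the scheduled time, and any pharmacokineticist would read the clause that way. That is probably right about intent. It does not make the written rule operative, and the correction is one word.

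Three stronger readings are tempting, and the documents do not support them.

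- *Every badly timed profile would be let through.* The fallback needs failed regression and Sponsor agreement, and data review can still remove a profile. The tolerance rejects nothing; the process as a whole can.
- *A profile that stops at 6 h on Day 1, or at 48 h in Part 1B, could be reported as AUCτ or AUC0-72.* The clause concerns a sample whose actual time differs from its scheduled time. A missing sample has no actual time, and at steady state it has its own substitution rule. The SAP nowhere says that an earlier scheduled sample may stand in for the last one.
- *The food-effect result is at risk.* Its declared endpoints are AUC0-tlast, AUC0-∞ and Cmax, none of which uses this rule. A mistimed Part 1B 24 h sample is normally bracketed by those at 10 h and 48 h, so the 24 h value can be interpolated without a terminal slope. A narrow route remains: AUCτ is in the mixed model, and SAP 16.1.5.1 allows a fixed-time AUC to replace an unreliable AUC0-∞.

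It is also fair that dose proportionality is exploratory and that SAP 16.1.3 itself urges caution in reading it.

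**Conclusion.** The point stands as a defect of wording in an operative analysis rule. The stated 10% tolerance excludes no mistimed end-of-interval sample, and no other passage supplies a numeric limit for a partial area computed without a usable slope. Case-by-case controls exist but set no threshold.

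The consequence is moderate and mostly confined to AUCτ in the Part 1A dose-proportionality and accumulation analyses. The illustrative loss of 5%, 12% and 19% for an 18 h sample rests on assumed half-lives of 5, 10 and 24 h and mono-exponential decline. The error can also run upwards if an over-long interval is used. How often the fallback would be reached cannot be judged from the documents, which state no half-life and do not define a suitable regression.

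**What to change.** In SAP 16.1.5.1, change the reference in the tolerance from the actual to the scheduled sampling time, and give the limits: 21.6 to 26.4 h for τ = 24 h and 64.8 to 79.2 h for 72 h. Add that:

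- outside these limits the actual-time fallback is not used;
- the steady-state substitution rule stays in force;
- for the alternate schedules in protocol Appendix 7, where an in-window 24 ± 4 h sample can be up to 16.7% off, the SAP states whether the 10% limit or the sampling window governs.

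A blanket instruction to report every other case as not calculable is not needed, and would cut across the substitution rule.

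The cost is two or three sentences in the SAP. A few partial areas may become non-calculable, which in cohorts of about three is a real but small loss. Part 1B samples taken within their ± 2 h windows are unaffected.
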